- I will ensure that any staff at my site(s) who are involved in the study conduct are adequately trained regarding this trial's operations, the protocol and their responsibilities. In the case of delegating any of my study responsibilities I will provide the sponsor with a delegation of investigators responsibilities log.
- I understand that the study may be terminated or enrollment may be suspended at any time by ViroMed, Co., Ltd. with or without cause, or by me or my institution if it becomes necessary to protect the best interest of the study patients.

Principal Investigator's Name (print)

Title

Address

Signature / Date

STUDY SYNOPSIS

PROTOCOL TITLE	A Phase II, Double-blind, Randomized, Placebo-controlled, Multicenter Study to Assess the Safety and Efficacy of VM202 in Subjects with Critical Limb Ischemia
STUDY PHASE	II
INVESTIGATIONAL AGENT	VM202
DOSE	Two doses will be tested: 8 mg and 16 mg of VM202.
POPULATION	Patients aged ≥ 18 years to ≤ 90 years diagnosed with critical limb ischemia (CLI).
STUDY DESIGN	
A phase II, double-blind, randomized, placebo-controlled, multicenter, 12-month study designed to assess the safety and efficacy of unilateral intramuscular injection in the calf of VM202 in patients with critical limb ischemia (CLI). Fifty (50) patients will be randomized in a 2:2:1 ratio to one of three treatment groups:
 
• Low Dose: 8 mg VM202 – 20 patients• High Dose: 16 mg VM202 – 20 patients• Control – placebo (normal saline) – 10 patients 
Up to twenty sites will participate in the study. Safety will be monitored throughout the study by a Data Safety Monitoring Board (DSMB).

STUDY OBJECTIVES	
1. To evaluate the safety of IM administration of VM202 in subjects with moderate or high-risk CLI (Rutherford Clinical Severity Score equal to 4 or 5) who are poor or non-candidates for surgical or percutaneous revascularization.2. To evaluate potential bioactivity of IM administration of VM202 in subjects with CLI, when compared with placebo, on rest pain (as assessed by frequency of rest pain, pain medication use history, sleeping history, and intensity of rest pain) or leg ulcer healing (as assessed by ulcer surface area, time to complete healing), perfusion (MRA), hemodynamic assessment (ABI & TBI), tissue oxygenation (TcPO₂) and the incidence and

extent of lower leg amputation or other surgical interventions

INCLUSION CRITERIA

1. Male or female, between 18 and 90 years of age;
2. Diagnosis of critical limb ischemia (Rutherford Class 4 or 5), including:
 - A resting ankle systolic pressure (in either the dorsalis pedis or posterior tibial arteries) of ≤ 70 mmHg in the affected limb; or
 - A resting toe systolic pressure of ≤ 50 mmHg in the affected limb; or
 - For patients in which measurement of ankle systolic pressure is not feasible (e.g. vessel calcification and non-compressibility), TcPO₂ ≤ 30 mmHg;
3. Poor or suboptimal candidate for bypass graft surgery or percutaneous angioplasty;
4. Pain at rest, and/or ischemic ulcers, and/or focal gangrene (< 3 cm²) for a minimum of 2 weeks,
5. Significant stenosis ($\geq 75\%$) of one or more of the following arteries: superficial femoral, popliteal, or two or more infra-popliteal arteries as verified by angiography within 12 months prior to enrollment;
6. Be willing to maintain current drug therapy for peripheral arterial disease throughout the course of the study including an anti-platelet, hypertension, and statin treatment unless not tolerated;
7. Clinically stable on optimized medical regimen for ≥ 30 days;
8. Be capable of understanding and complying with the protocol and signing the informed consent document prior to being subjected to any study related procedures;
9. Women who are surgically sterile or at least 1 year postmenopausal or who have been practicing adequate contraception for at least 12 weeks prior to entering the study. If the subject is of child-bearing potential, she must have a negative urine pregnancy test result prior to study enrollment and must agree to repeat pregnancy screening tests during the study. If the subject or the subject's partner(s) is of child bearing potential, the subject and the subject's partner(s) must agree to use a "double barrier" method of birth control while participating in this study.

EXCLUSION CRITERIA

1. Subjects who have undergone a successful revascularization procedure or sympathectomy within 12 weeks prior to study entry. A clinically *unsuccessful* revascularization procedure is defined as one in which:
 - the target vessel re-occludes ($\geq 50\%$, as verified by a second angiogram. Duplex ultrasonography can be used

-
- to determine vessel patency if the patient cannot tolerate a second angiogram), or
- the target vessel remains patent, but there is no resolution of symptoms 6 weeks after the procedure (e.g. no evidence of ulcer healing, no improvement in pressures, no reduction in resting pain);
2. Subjects that will require an amputation in the target leg within 4 weeks of randomization;
 3. Subjects with evidence of active infection (e.g., cellulitis, osteomyelitis) or deep ulceration exposing bone or tendon in the extremity planned for treatment;
 4. Heart Failure with a NYHA classification of III or IV;
 5. Stroke (NIH scale >2) or myocardial infarction within last 3 months;
 6. Unstable angina
 7. Uncontrolled hypertension defined as sustained systolic blood pressure (SBP) > 200 mmHg or diastolic BP (DBP) > 110 mmHg at baseline/screening evaluation;
 8. Ophthalmologic conditions pertinent to proliferative retinopathy or conditions that preclude standard ophthalmologic examination;
 9. Inflammatory disorder of the blood vessels (inflammatory angiopathy, such as Buerger's disease);
 10. Subjects with advanced liver disease including decompensated cirrhosis, jaundice, ascites or bleeding varices;
 11. Subjects currently receiving immunosuppressive medications chemotherapy, or radiation therapy;
 12. Positive HIV or HTLV at Screening;
 13. Active Hepatitis B or C infection as determined by Hepatitis B surface antibody (HBsAb), Hepatitis B core antibody (IgG and IgM; HBcAb), Hepatitis B surface antigen (HBsAg) and Hepatitis C antibodies (Anti-HCV), at Screening;
 14. Specific laboratory values at screening including: Hemoglobin < 8.0 g/dL, WBC < 3,000 cells per microliter, platelet count < 75,000/mm³, AST and/or ALT > 3 times the upper limit of normal or any other clinically significant lab abnormality which in the opinion of the investigator should be exclusionary;
 15. Patients with a recent history (< 5 years) of or new screening finding of malignant neoplasm except basal cell carcinoma or squamous cell carcinoma of the skin (if excised and no evidence of recurrence); patients with family history of colon cancer in any first degree relative are excluded unless they have undergone a colonoscopy in the last 12 months with negative findings;
 16. Elevated PSA unless prostate cancer has been excluded;

17. Subjects with any co- morbid conditions likely to interfere with assessment of safety or efficacy or with an estimated life expectancy of less than 6 months
18. Subjects requiring > 81 mg daily of acetylsalicylic acid; If > 81 mg are taken at screening, subjects may be enrolled if willing/able to switch to another medication for the duration of the study;
19. Subjects requiring regular COX-2 inhibitor drug(s) or high dose steroids (excepting inhaled steroids);
20. Major psychiatric disorder in past 6 months;
21. History of drug or alcohol abuse / dependence in the past 2 years;
22. Use of an investigational drug or treatment in past 12 months; concurrent participation in investigational protocol or unapproved therapeutics; and
23. Unable or unwilling to give informed consent.

STUDY PROCEDURES

Patients will be screened for study eligibility after giving informed consent. Screening should occur within the 60 days prior to Day 0 (day of injection). Screening will include assessment of study eligibility, a complete medical history, physical exam, cancer screening tests, viral screening, ABI & TBI, TcPO₂, VAS, 12 lead EKG, retinal fundoscopy, clinical chemistry, hematology, urinalysis, and pregnancy test (women of childbearing potential only), and documentation of any ulcers or gangrenous areas.

Patients will be treated with a final dose of 8 mg VM202, 16 mg VM202 or placebo by intramuscular injections in the affected calf on Day 0, Day 14, Day 28 and Day 42. VM202 will be delivered in a solution of 0.5 mg VM202 / mL.

TREATMENT GROUP	FINAL DOSE VM202	DOSE VM202 (MG) PER VISIT			
		DAY 0	DAY 14	DAY 28	DAY 42
Low Dose	8 mg	4	4	0	0
High Dose	16 mg	4	4	4	4
Placebo	0	0	0	0	0

Patients in the Low Dose Group (8 mg VM202) will receive:

- Day 0: 4 mg of VM202 (16 injections of 0.5 ml of VM202)
- Day 14: 4 mg of VM202 (16 injections of 0.5 ml of VM202)
- Day 28: Placebo only (16 injection of 0.5 ml normal saline)
- Day 42: Placebo only (16 injection of 0.5 ml normal saline)

Patients in the High Dose Group (16 mg VM202) will receive:

-
- Day 0: 4 mg of VM202 (16 injections of 0.5 ml of VM202)
 - Day 14: 4 mg of VM202 (16 injections of 0.5 ml of VM202)
 - Day 28: 4 mg of VM202 (16 injections of 0.5 ml of VM202)
 - Day 42: 4 mg of VM202 (16 injections of 0.5 ml of VM202)

Patients in the placebo control group will receive 16 injections of 0.5 ml normal saline at each visit.

Determination of HGF serum levels will be made immediately pre-treatment on Day 0, immediately pre-treatment on Day 42, Day 49 and Day 90.

The number of copies of VM202 in whole blood will be determined at Day 0 (pre-injection, and 2 hours post injection), Day 42 (pre-injection, and 2 hours post injection), Day 49, Day 90, and at 6 months.

VAS assessment will be performed at Day 0 (pre-injection), Day 14 (pre-injection), Day 28 (pre-injection), Day 42(pre-injection), Day 90, at 6 months, 9 months, and 12 months. VascuQoI will be administered on Day 0 (pre-injection), Day 90, at 9 months, and 12 months. . Rutherford classification will be determined at 6 months, 9 months, and 12 months. ABI & TBI will be recorded at Day 0 (pre-injection), Day 28 (pre-injection), Day 90, at 6 months, 9 months, and 12 months. TcPO₂ will be measured at Day 0 (pre-injection), 6 months, 9 months, and 12 months. Measurement of ulcer(s) will be performed at Day 0, Day 14, Day 28, Day 42, Day 49, Day 90, at 6 months, 9 months, and 12 months. Retinal funduscopy will be conducted at 12 months. Adverse events will be recorded throughout the one year follow-up period.

MRA will be conducted as a sub-study at up to two sites on Day 0 (pre-injection) and at 6 and 9 months.

SCHEDULE OF EXAMINATIONS

Screening (Day -60 to Day 0)

Day 0

Day 14 ± 3 days

Day 28 ± 3 days

Day 42 ± 3 days

Day 49 ± 3 days

Day 90 ± 7 days

Month 6 ± 1 month

Month 9 ± 1 month

Month 12 ± 1 month

STUDY ENDPOINTS

The primary study endpoint is to assess the difference in pain level between baseline and the 9 month follow-up as determined by VAS. Active and placebo arms will be compared to determine treatment effect.

Other secondary endpoints will include:

- Difference in pain level between baseline and the 9 month follow-up as determined by VAS by sex and by comorbidities (esp. diabetes or renal dysfunction)
- Change in tissue oxygenation (TcPO₂) from baseline to 6, 9 and 12 months following the first treatment
- Change in hemodynamic measures (ABI and TBI) from baseline to Day 28, Day 90, 6 months, 9 months and 12 months following the first treatment
- Change in perfusion (MRA) from baseline to 9 months following the first treatment
- Wound healing (no ulcer: change of skin condition, one ulcer: change of ulcer size, multiple ulcer: change of ulcer number) from baseline to 9 months following the first treatment
- Change in VAS score from baseline to Day 14, Day 28, Day 42, Day 90, at 6 months, 9 months, and 12 months.
- Change in QOL score (VascuQol) at 90 Days, 9 months and 12 months;
- Major limb amputation rate at six months and twelve months following the first treatment
- Mortality at six and twelve months after first treatment

SAFETY

Any patient who receives VM202 will be included in the safety analysis population. Adverse events (including serious adverse events, and adverse events leading to treatment discontinuation) throughout the 12 month follow-up will be described according to severity and their relationship to the study drug and / or device and procedure. Descriptive statistics (N, mean, median, SD, minimum and maximum values, where applicable) will be used to characterize safety parameters.

All patients will undergo testing as presented in the American Cancer Society Cancer Screening Guidelines as part of their baseline testing to rule out cancer.

TABLE OF CONTENTS

INVESTIGATOR’S AGREEMENT	2
STUDY SYNOPSIS	3
TABLE OF CONTENTS	9
GLOSSARY	13
PERSONNEL AND FACILITIES.....	15
1. BACKGROUND.....	18
1.1. Peripheral Arterial Disease.....	18
1.2. Critical Limb Ischemia.....	18
1.3. Treatment Options for CLI.....	18
1.3.1. Revascularization Options.....	19
1.3.2. Amputation.....	19
1.3.3. Unmet Clinical Need.....	19
1.4. Therapeutic Angiogenesis in Ischemic Limb Disease	19
1.5. VM202	20
1.6. Preclinical Data.....	21
1.7. Clinical Data	22
1.8. Study and Dose Rationale	23
2. GOOD CLINICAL PRACTICES STATEMENT	23
3. INVESTIGATIONAL PLAN.....	24
3.1. Study Objectives	24
3.2. Study Design.....	24
3.3. Patient Population	26
3.3.1. Inclusion Criteria	26
3.3.2. Exclusion Criteria	26
3.4. Study Procedures	28
3.4.1. Informed Consent.....	28
3.4.2. Patient Identification	28
3.4.3. Screening (Day -60 to Day 0).....	28
3.4.3.1. Screen Failures.....	29
3.4.4. Treatment Authorization	29
3.4.5. Randomization & Blinding.....	29
3.4.6. Day 0 – 1 st Injections	30
3.4.6.1. Pre-Injection (within 4 hrs prior to injections)	30
3.4.6.2. 1 st Dose of VM202 / Placebo.....	30
3.4.6.3. Post-Injection	30
3.4.7. Day 14 ± 3 Day –2 nd Injections	31
3.4.7.1. Pre-Injection (within 4 hrs prior to injections)	31
3.4.7.2. 2 nd Dose of VM202 / Placebo	31
3.4.7.3. Post-Injection	31
3.4.8. Day 28 ± 3 Day –3 rd Injections.....	31
3.4.8.1. Pre-Injection (within 4 hrs prior to injections)	31

3.4.8.2.	3 rd Dose of VM202 / Placebo	31
3.4.8.3.	Post-Injection	31
3.4.9.	Day 42 ± 3 Day – 4 th Injections	32
3.4.9.1.	Pre-Injection (within 4 hrs prior to injections)	32
3.4.9.2.	4 th Dose of VM202 / Placebo.....	32
3.4.9.3.	Post-Injection	32
3.4.10.	Day 49 ± 3 Days	32

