3.3.1. INCLUSION CRITERIA

1. Male or female, between 18 and 90 years of age;
2. Diagnosis of critical limb ischemia (Rutherford Class 4 or 5), including:
 - A resting ankle systolic pressure (in either the dorsalis pedis or posterior tibial arteries) of ≤ 70 mmHg in the affected limb; or
 - A resting toe systolic pressure of ≤ 50 mmHg in the affected limb; or
 - For patients in which measurement of ankle systolic pressure is not feasible (e.g. vessel calcification and non-compressibility), $TcPO_2 \leq 30$ mmHg;
3. Poor or suboptimal candidate for bypass graft surgery or percutaneous angioplasty;
4. Pain at rest, and/or ischemic ulcers, and/or focal gangrene (< 3 cm²) for a minimum of 2 weeks;
5. Significant stenosis ($\geq 75\%$) of one or more of the following arteries: superficial femoral, popliteal, or two or more infra-popliteal arteries as verified by angiography within 12 months prior to enrollment;
6. Be willing to maintain current drug therapy for peripheral arterial disease throughout the course of the study including an anti-platelet, hypertension and statin treatment unless not tolerated;
7. Clinically stable on optimized medical regimen for ≥ 30 days;
8. Be capable of understanding and complying with the protocol and signing the informed consent document prior to being subjected to any study related procedures;
9. Women who are surgically sterile or at least 1 year postmenopausal or who have been practicing adequate contraception for at least 12 weeks prior to entering the study. If the subject is of child-bearing potential, she must have a negative urine pregnancy test result prior to study enrollment and must agree to repeat pregnancy screening tests during the study. If the subject or the subject's partner(s) is of child bearing potential, the subject and the subject's partner(s) must agree to use a "double barrier" method of birth control while participating in this study.

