4.2.10. TRANSCUTANEOUS OXYGEN PRESSURE (TcPO₂)

Transcutaneous oxygen pressure (TcPO₂) will be measured at screening, before the first treatment (injection) on Day 0, at 6, 9 and at 12 months. TcPO₂ measurement sites will include the anterior and posterior calf and dorsum of the foot. Because TcPO₂ measurements are instrument dependent, investigators should use the same instrument for all TcPO₂ assessments and follow the standard procedures defined by their instrument's manufacturer. If a sensor placement site is unavailable due to amputation or areas of ulceration/gangrene, sensor placement site will be assigned a clinically equivalent default TcPO₂ value of zero pressure ("0 mmHg"). Hard copy instrumentation printout will be included in the source documentation to support the TcPO₂ data. The limb/chest TcPO₂ index will be calculated by using the lesser of the lower limb measurements.

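### A TcPO₂ value of 0 mmHg assigned to a covered sensor site may meet the entry threshold and, if it reaches the SAP analysis, distorts that site's change from baseline

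*Protocol*

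**What the plan says.** **Eligibility.** Inclusion 2 (Synopsis, repeated in Protocol 3.3.1) requires Rutherford class 4 or 5 and offers three haemodynamic routes joined by *or*: ankle pressure, toe pressure, and a third: "For patients in which measurement of ankle systolic pressure is not feasible (e.g. vessel calcification and non-compressibility), TcPO₂ ≤ 30 mmHg". Neither copy says which TcPO₂ site counts or that the value must be measured. Inclusion 4 admits ischaemic ulcers and small focal gangrene. Exclusion 3 removes only infected limbs and ulcers deep enough to expose bone or tendon.

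**Measurement.** On sites, Protocol 4.2.10 states: "TcPO₂ measurement sites will include the anterior and posterior calf and dorsum of the foot". On timing, TcPO₂ "will be measured at screening, before the first treatment (injection) on Day 0, at 6, 9 and at 12 months". The default is triggered as follows: "If a sensor placement site is unavailable due to amputation or areas of ulceration/gangrene". Then the "sensor placement site will be assigned a clinically equivalent default TcPO₂ value of zero pressure". No visit and no use of the value is exempted. The only rule there that combines sites takes the lowest limb value, and it is written for the limb/chest index.

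**Analysis.** Change in TcPO₂ "from baseline to 6, 9 and 12 months following the first treatment" is a secondary endpoint. SAP 10.2.2 analyses change from baseline separately for each body region, and again as a ratio to chest. Baseline is the Day 0 value if it differs from screening by no more than 15% of the screening value, and otherwise the average of the two. The SAP does not mention the 0 mmHg default. For a major amputation, SAP 10.2.2.1 (ITT) carries forward the value before amputation. SAP Listing 19 allows limb sites to be shown as not done.

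**The concern.** A default of zero may be a reasonable worst-case score when a limb deteriorates during follow-up. It does a different job at screening and Day 0. There, an imputed number can meet a numerical entry threshold that is meant to document poor perfusion, and it can become the baseline from which a gain is measured. Patients with both tissue loss and calcified ankle arteries are the ones likely to need the TcPO₂ route, so the two rules can meet in practice.

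For the endpoint, closure of a lesion over a sensor would appear as improved tissue oxygenation even if oxygenation at that site had not changed. Wound healing is a separate secondary endpoint, so the same event would be counted in both. With arms of 10 and 20 patients, a few such sites could visibly move a mean.

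**Working it through.** The documents give no figure for this point, so there is none to reproduce. The check applies the rules as written.

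**1. Does an assigned zero meet the threshold?** Inputs: threshold 30 mmHg (inclusion 2); default 0 mmHg and three limb sites (4.2.10). Assumed patient: ankle pressure not feasible, dorsum of the foot covered by an ulcer (0 mmHg), both calf sites measured at *c*. The mean of three sites is (0 + *c* + *c*)/3 = 2*c*/3.

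| Reading of inclusion 2 | *c* = 35 | *c* = 50 | *c* = 60 |
|---|---|---|---|
| Any site, or lowest site | 0: meets | 0: meets | 0: meets |
| Mean of three sites | 23.3: meets | 33.3: fails | 40.0: fails |
| All sites ≤ 30 | fails | fails | fails |
| Measured sites only | fails | fails | fails |

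Under the mean reading the patient meets the threshold up to *c* = 45, since 2 × 45/3 = 30. The result therefore depends on a choice that the criterion leaves open.

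**2. What does the SAP baseline rule do with a zero?** Percent difference = |Day 0 − Screening| / Screening × 100.

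| Screening | Day 0 | Percent difference | Baseline |
|---|---|---|---|
| 0 | 0 | 0/0, undefined | 0 on either branch |
| 0 | 25 | 25/0, undefined | 25 or (0 + 25)/2 = 12.5, depending on the branch |
| 25 | 0 | 25/25 = 100% | (25 + 0)/2 = 12.5 |

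The 25s are illustrative. In the second row the baseline depends on how the program handles division by zero. In the third, a site that reads 25 at follow-up shows a gain of 25 − 12.5 = 12.5 with no real change.

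**3. How far does one patient move an arm mean?** Shift = spurious change / *n*. Assumptions: screening and Day 0 both 0 by default; the lesion closes; the site then reads 20–40 mmHg; true change is nil; planned arm sizes apply.

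- Placebo, *n* = 10: 20/10 to 40/10 = 2 to 4 mmHg.
- Either active arm, *n* = 20: 20/20 to 40/20 = 1 to 2 mmHg.

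A site reading 20–40 mmHg at baseline and covered later scores −20 to −40, which gives shifts of the same size in the other direction.

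**4. Do the two documents treat the triggers alike?** After amputation, Protocol 4.2.10 gives 0 and SAP 10.2.2.1 (ITT) gives the prior value. For a site under an ulcer, the protocol gives 0, while Listing 19 would permit not done. These cannot all govern the same dataset.

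**The case against.** Several stronger readings are tempting, and the documents do not support them.

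- *The default passes the patient automatically.* This needs an any-site or lowest-site reading. The lowest-value rule in 4.2.10 belongs to the limb/chest index, not to inclusion 2. It also needs an ankle pressure that cannot be measured and a lesion that makes a calf or dorsum site unavailable; an ulcer elsewhere on the foot does not trigger the default.
- *The patient enters with no perfusion measurement.* ABI, TBI and TcPO₂ are all scheduled at screening, and the uncovered TcPO₂ sites would be read. What may be lacking is a measured TcPO₂ at or below 30 mmHg.
- *Patients with non-ischaemic ulcers are let in.* Inclusion 4 specifies ischaemic ulcers, inclusion 5 requires stenosis of at least 75% on angiography, Rutherford 4 or 5 is required, and Protocol 4.1.1 asks for a history that excludes other causes. The vascular/non-vascular code in SAP Listing 23 shows only that the distinction can be recorded.
- *The zero is false.* The protocol chose it deliberately and calls it clinically equivalent. Nothing in the documents shows what the true value would be.
- *The SAP uses a zero baseline.* SAP 10.2.2 never says so, and Listing 19 and the amputation rule point the other way.

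It is also fair that regions are analysed separately, that the convention applies alike in every arm, and that TcPO₂ is secondary.

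These objections limit the point but do not remove it. The default is mandatory wording that covers screening and Day 0, no text bars it from eligibility or baseline, and the SAP is silent where a rule is needed.

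**Conclusion.** The point holds in a limited form. Protocol 4.2.10 creates an imputed value at screening and baseline, and neither inclusion 2 nor SAP 10.2.2 says whether it counts. Under an any-site or lowest-site reading, it can meet the entry threshold without a measured TcPO₂ at or below 30 mmHg. If carried into the SAP, it turns lesion closure into a gain, and a new lesion into a loss, at the affected site, in its ratio to chest and in any lowest-site limb/chest index. The percent-difference baseline rule is undefined whenever screening is 0.

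The effect is 2–4 mmHg per affected patient in an arm of 10 and 1–2 mmHg in an arm of 20. This rests on an assumed post-healing reading of 20–40 mmHg and no true change. How many patients would be affected, and how they would split between arms, cannot be found in the documents. Other TcPO₂ regions and the primary VAS analysis do not use the value. The correction is cheap and should be made before the analysis is fixed.

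**What to change.** **SAP 10.2.2.** Base each site's change-from-baseline analysis on sites with a measured value at both baseline and the follow-up visit. Show the 0 mmHg default only as a sensitivity analysis. Define the baseline when screening is 0 or was not measured, and say whether a covered site counts as missing for the carry-forward rules in 10.2.2.1. Excluding only zero baselines would be one-sided, because it would remove the spurious gains and leave the spurious losses.

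**Inclusion 2 and Protocol 4.2.10.** Reconcile them by stating which site or sites decide eligibility and that an assigned, unmeasured 0 does not by itself meet the threshold. The threshold itself is not in question.

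**Amputation.** Reconcile 4.2.10 (zero) with SAP 10.2.2.1 (prior value), so that one rule governs each analysis.

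**Cost.** A few sentences in each document, slightly fewer site-level values, and possibly a few patients who no longer qualify by this route. A measured-only analysis also leaves out sites that became covered because the limb worsened. The sensitivity analysis should therefore be kept, and the number of covered sites reported by arm and visit.
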